#### 7.5 Reference test

The reference test is the final report from the CTC or colonoscopy examination and confirmatory histology report. Biopsies are required as per national guidance (4) in the investigation of participants with lower gastrointestinal symptoms even in the absence of macroscopic abnormalities.

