#### **STUDY SUMMARY**

	Objectives Outcome Measures
Planned study period	40 months
Sample size	1915
Study arms	All participants will receive the index tests: stool FIT and urine VOCs; and reference standard: full colonoscopy examination or CTC.
	Stool FIT and urine VOC
Reference standard Index tests	Final report from the CTC or colonoscopy examination and confirmatory histology report Stool FIT alone
Study participants	Participants referred from primary care to NHS Trusts that undertake colonoscopy or CTC will be approached to participate.
Study design	Multicentre – Prospective Diagnostic Accuracy Study
	*Significant Bowel Disease (SBD) is defined as those with colorectal cancer, significant pre-malignant polyps (adenomas with size >10mm or with high grade dysplasia)or inflammatory bowel disease
	If stool FIT plus urine VOC is sufficiently accurate it will enable a reduction in the number of colonoscopies and Computed Tomography Colonography (CTC) in those without SBD.
Study aim	To investigate the diagnostic accuracy of stool FIT plus urine VOC compared to stool FIT alone for detection of SBD*.
Research question	Can the addition of urine VOC to stool FIT testing rule out significant bowel disease (SBD) and by so doing, reduce unnecessary invasive tests (colonoscopy/CTC) – the right test for the right participant?
Study title	Reducing Colonoscopies in patients without significant bowEl DiseasE - RECEDE study

Primary	Diagnostic accuracy of stool FIT plus urine VOC compared to stool FIT alone to improve detection of SBD.	Sensitivity, specificity, negative predictive value (NPV) and positive predictive value (PPV) of stool FIT plus
		urine VOC in detection of SBD, using CTC or colonoscopy histology findings.
Secondary	Diagnostic accuracy of stool FIT plus urine VOC in detection of SBD	Receiver operating characteristic (ROC) curve of stool FIT plus urine VOC in detection of SBD.
	Impact on number of colonoscopies and CTCs undertaken	Calculation of potential number of colonoscopies and CTCs avoided in those without SBD.
	Cost effectiveness and colonoscopy/CTC disutility	Cost calculation, Quality of life (EQ-5D-5L) and quality adjusted life years (QALY) associated with utility of each diagnostic strategy (stool FIT and urine VOC)

Key Words:

FIT, urine VOC, diagnostic, colorectal cancer, adenoma, IBD, colonoscopy

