#### 1.6 Impact of COVID-19 on Patient pathways

COVID-19 has brought about a change in the way people who are experiencing lower GI symptoms are referred into secondary care (illustrated in Appendix C Figure 3). Previously, FIT testing would be used in some regions, and only on low risk patients (~10% of all patients) before they were referred to secondary care. They would then be referred for colonoscopy only if the FIT test was positive. However, in most regions and patients, a person presenting to their GP with GI symptoms would be referred either routinely or urgently in accordance with the NICE guidelines (4) without the need for a prior FIT test.

Since the outbreak of COVID-19 within the UK, hospitals have seen a drastic fall in the number of patients being referred with GI symptoms. However since lockdown measures have eased and at time of writing this protocol, we are now beginning to see a rise in the number of referrals, and there is a backlog to be cleared. To manage limited colonoscopy capacity due to the impact of COVID-19 and colonoscopy (which is a potential aerosol generating procedure), FIT may be used (outwith) NICE guidance to triage referrals to colonoscopy.

In addition there has also been a stark increase in the number of patients being referred for a CT scan instead of colonoscopy. Our preliminary data shows that over 25% of all GI referrals to secondary are currently having CT scans. CT scan is a radiological procedure that was often favoured for older patients with comorbidities as they are more at risk of adverse events during a colonoscopy. However, COVID-19 has caused a shift in practice, whereby more people are now being referred for CT scans, and this shift appears to be here to stay for the long term. CT scans are split into regular CTs and CTC, the latter of which has been shown to have similar sensitivity to colonoscopy for the detection of colorectal cancer (Halligan et al., 2005) and large polyps (Pickhardt et al., 2003). It is common for CTC positive patients to then have a colonoscopy to receive histological confirmation of any diagnosis. Some NHS Trusts have already adopted CT scans for 100% of referrals, using colonoscopy as only a confirmatory diagnostic follow up.

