#### 8.2.3 Secondary outcome analysis

To find the optimal threshold of FIT and VOC we will first plot the receiver operating characteristic (ROC) curves of both tests individually. The individual optimal threshold is the one that gives the greatest specificity whilst achieving the required 97% sensitivity to avoid colonoscopy or CTC. Secondly, we will plot combinations of the two tests in the ROC space and similarly, choose the combination of thresholds which has greatest specificity whilst achieving the required 97% sensitivity to avoid colonoscopy or CTC. The combined thresholds of FIT and VOC in the ROC space is done by combining every unit of FIT (from 7 to 120 µgHb/g faeces) with every unit of the predicted probability of VOC (from 0.63 to 1). Both the "or" and "and" rules will be used in combining the FIT and VOC results to define a case as positive (having SBD and requires colonoscopy) and negative (no SBD and does not require colonoscopy or CTC). The "or" rule is as described in Section 8.2.2. The "and" rule is when both FIT and VOC tests define a case as positive then the diagnosis is positive. If both tests are in discordant, i.e. only one of them defines a case as positive and the other defines it as negative then the diagnosis is negative. For each of the thresholds that we derive from the ROC curves, we will also report the NPV estimates. This will produce an overestimate of test accuracy, which we will use as a sensitivity analysis in the economic model, as a

more optimistic assumption to demonstrate the range of uncertainty. Similarly, the reference standard is the final report from the CTC or colonoscopy examination and confirmatory histology report of SBD.

Other secondary analyses include sensitivity, specificity, PPV and NPV estimates and their corresponding 95% CI for each individual condition of SBD (colorectal cancer, colorectal adenomasand inflammatory bowel disease) by each individual test and combination rules.

We will also estimate the compliance rates – return of stool and urine samples – by presence of SBD or not and individual conditions comprising SBD, as well as if samples are missing at random or not. All accuracy tests will be adjusted by covariates (demographics and/or clinical parameters) if there is an association between each covariate and the test results.

Appropriate procedures to account for the type of missing data will be performed for sensitivity analyses.

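### The protocol treats CTC and colonoscopy as one interchangeable reference standard for SBD, so disease that CTC misses enters the accuracy tables as no SBD, with the IBD-specific results most exposed

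*Protocol*

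**What the plan says.** - **Target condition.** The Study Summary defines SBD as colorectal cancer, "significant pre-malignant polyps (adenomas with size >10mm or with high grade dysplasia)or inflammatory bowel disease". High-grade dysplasia qualifies an adenoma of any size.
- **Reference test.** Section 7.5: "The reference test is the final report from the CTC or colonoscopy examination and confirmatory histology report". It continues: "Biopsies are required as per national guidance (4) in the investigation of participants with lower gastrointestinal symptoms even in the absence of macroscopic abnormalities". No exception is made for CTC.
- **Support for CTC.** Section 1.6 describes CTC as "the latter of which has been shown to have similar sensitivity to colonoscopy for the detection of colorectal cancer", then adds "and large polyps". IBD and smaller adenomas are not mentioned.
- **Histology after CTC.** Section 1.6: "It is common for CTC positive patients to then have a colonoscopy to receive histological confirmation of any diagnosis". Nothing comparable is said for CTC-negative participants.
- **Analysis.** Section 8.2.2 builds the primary 2x2 table on the pooled CTC-or-colonoscopy standard, and 8.2.3 carries it over. Section 8.2.3 also states: "Other secondary analyses include sensitivity, specificity, PPV and NPV estimates and their corresponding 95% CI for each individual condition of SBD". Under 8.3 the economic model is run separately for each SBD condition, with accuracy taken from RECEDE.
- **Different wording.** Section 8.2.1, and the missing-data rule in 8.2.2, name colonoscopy alone as the reference.
- **Follow-up.** Section 6.6 plans a record check of CTC participants for at least 52 weeks or until un-blinding. It recommends colonoscopy for CTC-negatives who are FIT or VOC positive and have had no further specialist lower GI care. The findings feed an exploratory count (1.2) and a count of cases missed by CTC (end of 8.2.3).

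**The concern.** A pooled reference standard is sound only if both examinations can establish every component of the target condition. For CTC the protocol makes that case for two components and leaves out IBD and small high-grade adenomas. A CTC-negative participant will ordinarily have no tissue, so the biopsy sentence in 7.5 cannot be met for that person.

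A case missed by CTC leaves the sensitivity denominator. If the dual test was positive, the case moves from true positive to false positive and lowers specificity and PPV. If the dual test was negative, it moves from false negative to true negative, so a real miss disappears and NPV rises. For a rule-out test the second error matters more. The safeguard is also weaker there: CTC-negatives with both index tests negative get the record check but no recommended colonoscopy.

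Section 1.6 says CT was often favoured for older patients with comorbidities, so the two reference groups are unlikely to be comparable.

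**Working it through.** **1. The protocol's own figure (8.1).** 200 SBD cases / 0.19 = 1,052.6, so 1,053 analysable; 1,053 / 0.55 = 1,914.5, so 1,915. This reproduces.

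**2. Inputs for an illustration.**
- From 8.1: 1,053 analysable, 200 with SBD (853 without), dual-test sensitivity 0.97, planned 95% CI width 0.05, FIT-alone sensitivity for IBD 0.85.
- Assumed, not in the documents: CTC share 25% to 50%; IBD 25% to 40% of SBD; CTC sensitivity for IBD 20% to 60%; true dual-test specificity 0.60. Section 1.6 reports over 25% for CT scans of any kind and 100% at some Trusts, so it does not give the CTC share.
- Small high-grade adenomas are left out, because the documents give nothing to size them.

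**3. IBD cases recorded as no SBD.** Hidden = 200 x CTC share x IBD share x (1 - CTC sensitivity for IBD).
- Low: 200 x 0.25 x 0.25 x 0.4 = 5 of 50 IBD cases (10%), leaving 195 observed SBD cases.
- High: 200 x 0.5 x 0.4 x 0.8 = 32 of 80 IBD cases (40%), leaving 168.

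**4. High scenario, dual sensitivity 0.85 in all IBD and 0.97 in other SBD.** The 0.85 is a floor, because under the either-positive rule VOC can only add detections.
- True: TP = 120 x 0.97 + 80 x 0.85 = 184.4; FN = 15.6; TN = 853 x 0.60 = 511.8; FP = 341.2.
- Hidden cases: 32 x 0.85 = 27.2 move from TP to FP; 4.8 move from FN to TN.
- Observed: TP = 157.2; FN = 10.8; FP = 368.4; TN = 516.6.

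| Measure | True | Observed | Change (points) |
|---|---|---|---|
| Sensitivity | 184.4/200 = 0.922 | 157.2/168 = 0.936 | +1.4 |
| Specificity | 0.600 | 516.6/885 = 0.584 | -1.6 |
| NPV | 511.8/527.4 = 0.970 | 516.6/527.4 = 0.980 | +0.9 |
| PPV | 184.4/525.6 = 0.351 | 157.2/525.6 = 0.299 | -5.2 |

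The low scenario on the same basis gives sensitivity 188/200 = 0.940 true against 183.75/195 = 0.942 observed (+0.2), specificity -0.3, NPV +0.1 and PPV -0.8.

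**5. If the dual test is equally good for IBD.** With 0.97 in every component, observed and true sensitivity are both 0.970 however many cases are hidden. In the high scenario 31.04 hidden cases become false positives and 0.96 become true negatives. Observed specificity is (511.8 + 0.96)/885 = 0.579 (-2.1). PPV goes from 194/535.2 = 0.362 to 162.96/535.2 = 0.304 (-5.8).

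**6. Upper bound for sensitivity.** Suppose the IBD that CTC misses is also harder for FIT and VOC (0.85) than the IBD it sees (0.97). High scenario: true FN = 0.03 x 168 + 0.15 x 32 = 9.84, so true sensitivity is 0.951 against 0.970 observed (+1.9). The IBD-specific figure would be 0.97 observed against (48 x 0.97 + 32 x 0.85)/80 = 0.922 true (+4.8). The documents offer no evidence for this differential.

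**7. The other reading.** If the colonoscopy-only wording in 8.2.2 removes CTC-only participants, an assumed 25% CTC-only share leaves 0.75 x 1,053 = 790 analysable and about 150 cases. The interval width grows by roughly the square root of 200/150, from 0.05 to about 0.058.

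**The case against.** - **Missed SBD is anticipated.** Section 6.6 looks for lower GI diagnoses that CTC did not pick up, 1.2 counts later SBD as well as microscopic colitis, and 8.2.3 counts cases missed by CTC. A reader might infer that the protocol overlooks the problem; it does not. What stands is that none of these steps revises the primary or IBD-specific tables.
- **Not every missed case becomes an index-test error.** A reader might infer this, or that all IBD in the CTC group is lost. Only index-positive misses become errors; index-negative ones are hidden. Disease seen on CTC commonly goes on to colonoscopy and histology.
- **The classification is inferred.** No sentence says that a negative CTC means no SBD, and the colonoscopy-only wording allows another reading. This is fair, but that reading costs cases, so either way the text needs settling.
- **The sizes are assumed.** With the 86% in 1.9 for both FIT and VOC in IBD, and conditional independence, dual sensitivity is 1 - 0.14 x 0.14 = 0.98 and the upward bias in sensitivity vanishes. This stands.
- **The SAP may handle it.** Results by modality are typical SAP content, so one cannot conclude that none are planned. But the reference standard, the biopsy sentence and the conflicting wording are fixed in the protocol itself.
- **The biopsy sentence plainly concerns colonoscopy.** Probably so; that part needs only clarification.

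**Conclusion.** The point holds as a defect in how the reference standard is fixed. The protocol pools two examinations, justifies one of them for only part of SBD, states a biopsy requirement that CTC-negatives cannot meet, and names the reference standard in two ways.

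The direction is clear: specificity and PPV fall, NPV rises, and sensitivity is essentially unchanged or rises. The size is not known from the documents. Under the assumptions shown, pooled sensitivity, specificity and NPV move by about 0 to 2 points, within the planned CI width of 5 points; PPV can fall by up to about 6. A reader might infer that the primary sensitivity is materially inflated. The documents do not support that, since the bias is nil if the dual test performs as well in IBD as elsewhere.

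The IBD-specific table is affected most, losing 10% to 40% of its cases under the same assumptions and passing its estimates to the economic model. The change should be made, but the pooled primary analysis need not be abandoned.

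**What to change.** 1. Reconcile 6.6, 7.5, 8.2.1 and 8.2.2. State whether CTC-only participants enter the primary table, how a CTC-negative participant without histology is classified, and that the biopsy sentence concerns colonoscopy.
2. Keep the pooled primary table. Alongside it, report sensitivity, specificity, NPV and PPV by first reference modality, and pre-specify a sensitivity analysis in participants whose first reference test was colonoscopy.
3. Take the IBD-specific estimates in 8.2.3, and the IBD inputs to the model in 8.3, from that same group, with the pooled estimate beside them. Do not admit people to the group because of a later colonoscopy after CTC: that depends on the CTC result (1.6) and the index result (6.6), and would bring in verification bias.
4. As a further sensitivity analysis, reclassify CTC-negatives who have SBD in the record follow-up, noting that the recommended later colonoscopy is triggered by a positive index test.

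**Cost.** Wording and analysis time only; 7.7 already collects the CTC, colonoscopy and histology reports. The colonoscopy-first group would be smaller (25% to 50% fewer at the assumed CTC shares) and probably younger and fitter, so its intervals are wider and its estimates generalise less well. That is why it supplements the pooled primary table and does not replace it.

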#### 7.6 Data collection and management

The research team will make every effort to contact participants who have failed to submit the samples or attend the endoscopic procedure. They will schedule a maximum of 3 reminders over a 3 week period for the participant. Attempts to contact such participants will be documented in their records (e.g. times and dates of attempted telephone contact). To ensure questionnaires are completed at the correct time points research nurses will call participants to remind them or schedule email reminders if the participant has chosen to complete their questionnaire online.

The diagnosis from the colonoscopy or CTC examination, stool FIT and urine VOC will be collected by the research team once a diagnosis is confirmed.

#### 7.7 Data collection tools and source document identification

Quantitative data on FIT and urine VOC scores will be collected together upon analysis on the eCRF with demographics, baseline characteristics and meta-data. Data will be collected from participants while they are in the clinic, GP referral letters, hospital records, CTC and colonoscopy and histology reports.

A case report form (CRF) either electronic or paper with individual (anonymised) participant data will be used to record data as required for the study protocol. The data can be collected on the paper CRF first and then entered on the database, or entered directly on the online validated, GCP compliant, electronic data capture (EDC) system by each research team at their respective site. Individual user login access to this database will be granted to only those in the study team that require it for the performance of their role. Screening and recruitment logs of all participants approached to take part, and enrolled in the study will be held at each site. This will be stored in a password protected NHS computer. No participant personal data will be shared between sites. The collected data is used for the statistical analysis of the RECEDE study.

Each PI/recruiting site must ensure to keep records of all participating participants (sufficient information to link records e.g., CRFs, hospital records and samples), all original signed informed consent forms and all copies of the CRF pages which will be kept in the site file in a locked cabinet. Equally to ensure use of unambiguous participant identification codes that allows identification of all the data reported for each participant.

#### 7.8 Data handling and record keeping

All data will be kept on a central server system hosted by the sponsor and supported by the IT department to include security measures and back up of all files. Individual sites will be required to send scanned copies of their paper CRFs to the lead site periodically. Original copies will be are to be kept at the site and archived following study close out.

The sponsor will use an unambiguous participant identification code that allows identification of all the data reported for each participant.

Database validation and data entry checking procedures will be detailed in the Data Management Plan.

#### 7.9 Access to Data

Direct access will be granted to authorised representatives from the Chief Investigator, Sponsor, host institution and the regulatory authorities to permit study-related monitoring, audits and inspections - in line with participant consent. Participant personal data will only be accessed by those members of the study team that require it for the performance of their role.

#### 7.10 Archiving

Following the resolution of queries and confirmation of study close-out by the Chief Investigator, all essential documentation will transferred to a third party archiving service, which provides suitable fire and water-resistant facilities. Study files will be archived for a period of 25 years. Access to the study documentation will be restricted to named individuals within the study team with express permission from the Chief Investigator.

#### 7.11 Study assessments

See details and schedule events as detailed in Table 1.

#### 7.12 Storage and analysis of samples

Stool samples will be posted directly to the Rugby Bowel Cancer Screening Hub. Urine sample storage and transfer is described above in section 6.

#### 7.13 End of study definition

The study will end once the full 1915 participants have been recruited when the last participant completes their last follow-up assessment. The Sponsor and Chief Investigator reserve the right to terminate the research on safety grounds at any time. Before terminating the research, the sponsor and investigators will ensure that a review of the overall benefit-risk analysis confirms the balance to be no longer acceptable. Should termination be necessary both parties will arrange the relevant procedures which include informing the Research Ethics Committee. On termination of the research, the sponsor

and CI's will ensure that adequate consideration is given to the protection of enrolled participants interests.

The study will be stopped prematurely if:

- Mandated by the Ethics Committee
- Following recommendations from the Trial Steering Committee (TSC)
- Funding for the study ceases

The Research Ethics Committee will be notified in writing if the study has been concluded or terminated early. As this is an observational study with no planned intervention it is thought that there won't be any compelling circumstances which require early termination.

#### 8 STATISTICS AND DATA ANALYSIS

8.1 Sample size calculation

To replace colonoscopy and CTC the new testing strategy requires very high sensitivity to avoid false negative results and missed disease. False positive results are also undesirable, but these participants would simply follow the colonoscopy testing pathway that all participants follow currently. Therefore, the sample size calculations are based on achieving acceptable sensitivity. There are some data on the utility of FIT alone and urine VOC alone in the detection of SBD(6, 10, 37). Our recent study (n=562) is the only published study that evaluated the combination of both FIT and urine VOC for the detection of colon cancer, which was 97% (95% CI: 90 to 100), similar to that for colonoscopy(6). The sensitivity of FIT alone in detecting IBD is 0.85, with the combined accuracy of FIT and VOC unknown. On the basis of these previous studies, and the necessity for high sensitivity to replace colonoscopy, we assumed that the sensitivity (Se) of the FIT and urine VOC tests to detect SBD would be at least 0.97 which is very near 1.0. The confidence interval for such high sensitivity has to be adjusted such that the interval does not exceed 1.0. One recommended method is to use the Zhou-Li method as described in equations 4.5 to

replaced by Se. Assuming that the sensitivity of FIT and VOC to be at least 97% then for Se = 0.97 and a 95% CI width of 0.05 (ensuring a high precision around the sensitivity estimate) the required number of participants with SBD is 200. Further assuming that the prevalence of SBD in the population with bowel symptoms is 19% (likely underestimate), then 1053 participants are required. Based on previous study(6) about 55% of the participants would return both stool and urine samples and sufficient for FIT and VOC analyses. Thus, the total sample size required is 1,915.

This strategy is robust to changes in the underlying assumptions of test accuracy. Confidence intervals for sensitivity for different observed sensitivity for 150, 200 and 250 cases of SBD are shown in Figure 5(a). For the target sensitivity of 0.97, the width of the confidence interval is 0.05 with 200 SBD participants, with narrower and wider confidence interval limits, when the observed sensitivity is above and below this value, respectively (Figure 5(b)).

Figure 5 Confidence intervals for different estimates of sensitivity for 150, 200 and 250 cases of SBD.

This sample size is also robust to NPV (Figure 6), an outcome that is of interest as a high NPV suggests that participants without SBD would avoid having colonoscopy examination.

**Figure 6** Confidence intervals for different estimates of NPV for 400, 500 and 600 negative cases of SBD from 1000 samples.

